	TITLE: RETROSPECTIVE EXPERIENCE OF CIED IMPLANTATION WITH PIEDMONT ATHENS REGIONAL ELECTROPHYSIOLOGY	Revision	C
		Page 4 of 9	

Study Synopsis

COMPANY	Aziyo Biologics, Inc.
PROTOCOL No.	CPR-2212
PRODUCT(S)	CanGaroo® Envelope and Tyrx™ Absorbable Antibacterial Envelope
PROTOCOL TITLE:	Retrospective Experience of CIED Implantation with Piedmont Athens Regional Electrophysiology
OBJECTIVE	The objective of this study is to retrospectively gather information on patients who underwent a CIED procedure with either a CanGaroo, Tyrx envelope, or no envelope.
DESIGN	A single center will retrospectively review up to 700 subjects who underwent implantation of a CIED with CanGaroo, Tyrx, or no envelope. All sets of subjects enrolled will also be examined for any follow-up visits and/or adverse events that occurred up to 12 months post-surgery.
STUDY POPULATION	Male or female patients who underwent a CIED implantation utilizing CanGaroo hydrated in saline, CanGaroo hydrated in Antibiotic, Tyrx, or no envelope.
ENDPOINTS	The endpoints will be defined as: 
 1. The incidence of major infection post procedure. 2. Any pocket related issues that prompted an office visit
CLINICAL PARAMETERS	The following clinical data will be collected 
 • Demographic information • Risk factors for infection • Surgical procedure • Type of device implanted • Envelope soak solution used • Post procedure information on major infections as defined below • Post procedure information on pocket related issues • Post procedure information on hematoma
DURATION	Data will be collected for a minimum of one post-surgical visit after CIED implant for all groups. If more visits are available, data from those visits will be collected up to 12 months post-procedure.
CENTERS	Single center in the U.S.

	TYPE: Protocol	Document	CPR-2212
	TITLE: RETROSPECTIVE EXPERIENCE OF CIED IMPLANTATION WITH PIEDMONT ATHENS REGIONAL ELECTROPHYSIOLOGY	Revision	C
		Page 5 of 9	

1. Introduction and Rationale

This document is a protocol for a human research study. This study is to be conducted according to U.S. and international standards of Good Clinical Practice in accordance with applicable Federal regulations, International Conference on Harmonization guidelines, and institutional research policies and procedures.

Broader indications for the implant of cardiac implantable electronic devices (CIED) and population aging are the main reasons for the continuous increase in the use of pacemakers, implantable cardioverter-defibrillators, and devices for cardiac resynchronization therapy. The rate of infection is out of proportion to the increase in implantation rate. This is primarily due to the comorbidities in CIED patients, the greater complexity of the devices, and the increased duration of procedures.^{1,2,3}

2. Study Design and Methods

Clinical records will be reviewed and data collected for up to 700 subjects who underwent implantation of a CIED. All sets of subjects will have data reviewed for any visits on or after March 27, 2017. No subject will be excluded from the study based on gender, racial, or ethnic origin. Patients will not be contacted and only de-identified data will be collected. A waiver of Informed Consent and HIPAA authorization will be requested from the IRB.

Each patient's medical records will be reviewed by the investigator or designated personnel for basic clinical data, including demographic information, risk factors for infection, information about the surgical procedure, type of device implanted, and post procedure information on infection, pocket related issues, and hematoma information will all be collected for each subject. Data will be collected retrospectively using Electronic Data Capture (Medrio).

CIED infections are defined as (1) superficial cellulitis in the region of the CIED pocket with wound dehiscence, erosion, or purulent drainage, (2) deep incisional or organ/space (generator pocket) surgical site infection that meets the Centers for Disease Control and Prevention criteria, independent from time of surgery, (3) persistent bacteremia, or (4) endocarditis.

Major CIED infections are defined as a CIED infection resulting in one or more of the following:

- CIED system removal
- Any invasive procedure (e.g., pocket opened) without system removal

	TYPE: Protocol	Document	CPR-2212
	TITLE: RETROSPECTIVE EXPERIENCE OF CIED IMPLANTATION WITH PIEDMONT ATHENS REGIONAL ELECTROPHYSIOLOGY	Revision	C
		Page 6 of 9	

- Treatment with antibiotic therapy if the subject is not a candidate for system removal and infection recurrence after completion of antibiotic therapy or evidence of deep infection with wound dehiscence, erosion, or purulent drainage
- Death

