2.1 Schedule of Assessments

	Pre-Procedure Screening Visit	Procedure Visit	Follow-up Visits (up to 12 mo.)	Unscheduled Visit
Inclusion Determination	X			
Baseline Demographics	X			
Medical History/Risk Factors	X			
Type of Device Implanted		X		
Envelope Soak Solution Used		X		
Procedure Details		X		
Documentation of Complications		X		
Post-Operative Events			X	X
Infection Information/Culture Results			X	X
Pocket Related Issues			X	X

	TYPE: Protocol	Document	CPR-2212
	TITLE: RETROSPECTIVE EXPERIENCE OF CIED IMPLANTATION WITH PIEDMONT ATHENS REGIONAL ELECTROPHYSIOLOGY	Revision	C
		Page 7 of 9	

3. Study Objectives

The objective of the study is to:

1. The objective of this study is to retrospectively gather information on patients who underwent a CIED procedure with either a CanGaroo, Tyrx envelope, or no envelope.

Endpoints

The endpoints are defined as:

1. The incidence of major post procedure infection (as defined above)
2. Any pocket related issues that prompted an office visit which include but are not limited to pain, swelling, redness, migration and/or hematoma

4. Risks and Benefits

4.1.Risks

As this is a retrospective study, there are no physical potential risks to research subjects. There may be risks associated with loss of privacy.

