4.2. Benefits

As this is a retrospective study, there are no physical benefit to individual research subjects; however, society and physicians will benefit from the knowledge gained.

5. Data Analysis

Since this is a retrospective study, analyses will consist of tabulated data and descriptive statistics. Subject data listings and tabular and graphical presentations of the summary and statistical results will be provided. Additional quantitative and qualitative comparisons will be made between the groups of subjects, contemporary literature, and similar studies.

Statistical comparisons between treatment groups (CanGaroo versus Tyrx versus no envelope) will be performed using Fisher's exact test or Chi-square tests for categorical variables. Continuous variables will be analyzed using ANOVA. A log rank test will be performed to compare the time to infection between the CanGaroo, Tyrx, and no envelope treatment groups at all of the follow-up visits.

	TYPE: Protocol	Document	CPR-2212
	TITLE: RETROSPECTIVE EXPERIENCE OF CIED IMPLANTATION WITH PIEDMONT ATHENS REGIONAL ELECTROPHYSIOLOGY	Revision	C
		Page 8 of 9	

6. Ethical Considerations

6.1. *Code of Conduct*

The Investigator will ensure that the clinical study is conducted in accordance with good clinical practice and all regulatory and institutional requirements, including those for subject privacy, informed consent, Institutional Review Board, or Ethics Committee approval, and record retention.

6.2. *Institutional Review Board Approval and Oversight*

This protocol, or any subsequent modifications, will be reviewed and approved by an Institutional Review Board. A Waiver of Informed Consent and HIPAA due to the retrospective nature of this study will be requested.

The confidentiality of the identity of subjects enrolled in the study and the information contained in their study records will be maintained. Any publication of any data collected as part of this trial will only use de-identified data, so that identification of any individual subject will not be possible.

The records will be made available as required for review by the FDA, or other applicable regulatory agency and a reviewing IRB; however to the extent possible, the subject's identity will not be disclosed.

A subject identification number will be used during data collection and the patient name, date of birth, medical record number and/or address will NOT appear anywhere.

	TYPE: Protocol	Document	CPR-2212

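### Does the synopsis restrict infection data to major infections, against Section 2, the schedule and the log-rank test?

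*Combined protocol and SAP*

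**What the plan says.** Three places in the protocol describe the infection data to be abstracted.

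- Study Synopsis, clinical parameters: "Post procedure information on major infections as defined below".
- Section 2: "post procedure information on infection, pocket related issues, and hematoma information will all be collected for each subject".
- Schedule of Assessments (2.1), marked for follow-up and unscheduled visits: "Infection Information/Culture Results".

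Section 2 defines two nested events. The wider one begins: "CIED infections are defined as (1) superficial cellulitis in the region of the CIED pocket with wound dehiscence, erosion, or purulent drainage", and goes on to deep or organ/space infection, persistent bacteremia and endocarditis. The narrower one reads: "Major CIED infections are defined as a CIED infection resulting in one or more of the following", followed by four consequences. Endpoint 1 is the incidence of major infection, in both the synopsis and Section 3. Section 5 adds: "A log rank test will be performed to compare the time to infection between the CanGaroo, Tyrx, and no envelope treatment groups".

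**The concern.** The synopsis names the narrow event where Section 2 and the schedule name the wide one, and the protocol itself treats the two as different. A superficial infection with purulent drainage that leads to none of the four consequences is a CIED infection but not a major one.

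The scope of collection is settled when the Medrio form is built and the charts are read, before any analyst sees data. If the synopsis governed, chart reviewers would decide major status on the spot, and a case they judged non-major would leave no infection record. Major-infection calls could then not be rechecked from the study data, and an analysis of any infection would need the charts reopened. The bare word infection in Section 5 adds to the doubt, because it could be read as the wide event while endpoint 1 is the narrow one.

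**Working it through.** The documents give no infection rate, group sizes, alpha or power, so there is no figure of the plan to reproduce. The check is a comparison of texts.

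**1. How far the lists differ.** The synopsis list has eight items. Section 2 has seven, in the same order, omitting envelope soak solution. Of the seven shared items (demographics, risk factors, surgical procedure, device type, infection, pocket issues, hematoma), six agree in scope and one differs.

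**2. Whether any list is exhaustive.** None is. Section 2 omits soak solution, which the synopsis and the schedule both collect. The synopsis omits culture results, which the schedule collects. The lists are summaries that complete one another, so one synopsis item is weak evidence that something is excluded. The item also contains no word such as only.

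**3. Which practice satisfies all three texts.** Every major infection is a CIED infection, so:

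| Practice | Synopsis item | Section 2 | Schedule 2.1 |
|---|---|---|---|
| Abstract all CIED infections | met | met | met |
| Abstract major infections alone | met | not met | not met |

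Only the first row complies throughout. The texts are compatible, and together they lead to the wide collection.

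**4. Whether the definition can be applied without the wide data.** A major infection is a CIED infection plus a consequence. The reviewer must establish the infection first and then look for the consequence, so the wide record is the natural input to endpoint 1.

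**5. What else would hold a non-major case.** The synopsis design row has all subjects examined for "any follow-up visits and/or adverse events that occurred up to 12 months post-surgery". The schedule has separate rows for post-operative events and for pocket issues at the same visits. These are not tied to infection type, but they do not fit a plan that ignores non-major events.

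**6. The log-rank event.** Endpoint 1 is the only infection endpoint, and it is major infection in both places where it is stated. An analyst would use that event. With all infections abstracted, either version can be run and labelled.

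**7. Size in the worst case.** With N patients, CIED infection risk r and major share f, the number of patients whose infection record depends on the reading is N × r × (1 − f). The documents give only N, at most 700. Assuming r of 1% to 5% and f of 50% to 75%, the result runs from 700 × 0.01 × 0.25 = 1.75 to 700 × 0.05 × 0.50 = 17.5, or about 2 to 18 patients. This applies only if the form was built from the synopsis item against Section 2 and 2.1. Otherwise the number is zero.

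**The case for a change.** The strongest reply is that the synopsis wording looks deliberate, since it points to the definition of major infection and is the only infection-outcome item in that list. No statement in the available text says that the body overrides the synopsis. The error would also be one-sided: all infections can later be narrowed to major ones, but cases never abstracted cannot be recovered without returning to the charts. Adverse-event and pocket-issue records need not carry infection type or culture result, and bacteremia or endocarditis may not present at the pocket. The records are "reviewed by the investigator or designated personnel for basic clinical data", so the major call may rest on one reading of the chart.

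Part of this stands. The wording does differ, and Section 5 names neither the event nor its date. The date can matter even when the event is agreed, because major status depends on a later consequence. But choosing that date is a trade-off: dating by the consequence places events later than onset and loses those whose consequence falls after 12 months. The harm from the synopsis wording needs a form that departs from Section 2 and the schedule, and nothing in the documents suggests that one was built.

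**Conclusion.** This is a wording mismatch between a synopsis and its body, with no demonstrated effect on any result, and no change to the plan follows. It concerns one of seven shared list items. Following Section 2 and 2.1 as written also fulfils the synopsis, and analysts can settle the Section 5 event sensibly by taking it from endpoint 1. The stakes are limited further because the analyses are mainly descriptive and no alpha is stated. The endpoint 1 comparison is the same under either reading if the major calls are right.

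The conclusion rests on three assumptions: the Medrio form follows Section 2 and the schedule, major status is assigned by the Section 2 definition, and the report states which event the log-rank test used.

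### No determinant of the pocket-issue endpoint, such as antithrombotic use, is named at baseline, and the envelope groups are compared on it without adjustment

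*Combined protocol and SAP*

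**What the plan says.** **Outcomes.** The Endpoints part of section 3 defines endpoint 2 as "Any pocket related issues that prompted an office visit which include but are not limited to pain, swelling, redness, migration and/or hematoma". Hematoma is also a separate item under Clinical Parameters in the Study Synopsis: "Post procedure information on hematoma".

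**Baseline and procedure data.** Section 2 describes the abstraction as "including demographic information, risk factors for infection, information about the surgical procedure, type of device implanted", plus the post-procedure outcomes. The Synopsis lists "Risk factors for infection" beside demographics, surgical procedure, device type and soak solution. The schedule in section 2.1 has a row "Medical History/Risk Factors" and a row "Procedure Details". Neither is broken down into variables, and no available text names anticoagulants, antiplatelets or concomitant medication.

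**Analysis.** Section 5 states that comparisons of CanGaroo, Tyrx and no envelope "will be performed using Fisher's exact test or Chi-square tests for categorical variables". Continuous variables get ANOVA, and time to infection gets a log rank test. No regression, stratification, matching or propensity method is specified for either endpoint.

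**The concern.** The envelope groups were formed by past practice, not by randomization, so they may differ in ways that bear on the outcome. For infection, the plan at least commits to recording risk factors. For endpoint 2 it makes no matching commitment, although the endpoint includes hematoma and swelling, for which antithrombotic use is a plausible determinant.

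If patients on anticoagulants or antiplatelets received one envelope more often, that envelope would be charged with their hematomas. The planned tests cannot separate the two effects. Adding regression on infection risk factors alone might not help either, because those factors are chosen for the other endpoint.

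Timing matters too. Section 2 says that the data are de-identified, section 6.2 keeps the medical record number out of the data, and the available text describes no key back to the chart. A field missed at abstraction may be hard to recover later.

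**Working it through.** The plan gives no event rate, effect size, alpha, power or group sizes, so it has no figure of its own to reproduce. The check has a textual part and an illustrative part.

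**1. Lists against endpoints**

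| Item | Named by purpose or content? | Where |
|---|---|---|
| Infection risk factors | Yes, as a category, not itemized | Synopsis; section 2 |
| Pocket-issue or hematoma determinants | No | – |
| Antithrombotic use | Not named | – |
| Medical history | Row heading only | Section 2.1 |
| Demographics, procedure, device type | Yes | Synopsis; sections 2 and 2.1 |
| Soak solution | Yes | Synopsis; section 2.1 |
| Adjustment for any of these | None specified | Section 5 |

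**2. Size of the possible bias (all inputs assumed)**

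Let the pocket-issue risk be r0 without antithrombotic use and RR × r0 with it, let the prevalence of use be qa and qb in two groups, and let the envelope have no effect. The risk in a group is r0 × [1 + (RR − 1)q]. The r0 cancels, so the spurious risk ratio is [1 + (RR − 1)qb] / [1 + (RR − 1)qa].

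| RR | 30% v 50% | 30% v 60% | 20% v 70% |
|---|---|---|---|
| 1.5 | 1.25/1.15 = 1.09 | 1.30/1.15 = 1.13 | 1.35/1.10 = 1.23 |
| 2 | 1.50/1.30 = 1.15 | 1.60/1.30 = 1.23 | 1.70/1.20 = 1.42 |
| 3 | 2.00/1.60 = 1.25 | 2.20/1.60 = 1.38 | 2.40/1.40 = 1.71 |

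With equal prevalence the ratio is 1.0 whatever the RR.

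**3. Chance of a false signal (illustrative)**

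Further assumptions: 700/3 ≈ 233 per group (700 is the protocol's cap; equal split assumed), r0 of 3% or 5%, and a pairwise test at two-sided 5% by normal approximation, so nominally 2.5% in one direction.

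Example with r0 = 3%, RR = 3 and 20% v 70%:
- Risks: 0.03 × 1.4 = 0.042 and 0.03 × 2.4 = 0.072; difference 0.030; pooled risk 0.057.
- Standard error: √(2 × 0.057 × 0.943 / 233) = 0.0215, so z = 0.030 / 0.0215 = 1.40.
- Probability of passing 1.96 ≈ Φ(1.40 − 1.96) = Φ(−0.56) ≈ 0.29.

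Over RR 1.5 to 3 and both values of r0, the probability in the direction of the bias is:
- 30% v 50%: about 4% to 11%
- 30% v 60%: about 4% to 20%
- 20% v 70%: about 6% to 45%

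**4. Events available for adjustment**

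In the 20% v 70% scenarios the group risks run from 0.033 to 0.12, so expected events per group run from 233 × 0.033 = 7.7 to 233 × 0.12 = 28. That supports only a few covariates.

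**The case against.** Several points on the other side are sound, and they limit what can be said.

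- **A reader might infer that only infection risk factors are collected.** The documents do not support that. Demographics, procedure information, device type and soak solution are listed too, and some may bear on pain, swelling, migration or hematoma.
- **A reader might infer that antithrombotic use is not captured.** That is not shown. The section 2.1 row is not restricted to infection, the list in section 2 is introduced with open wording, and infection risk factors are not itemized either. The case report form is not among the documents, and part of the text just before section 2.1 was not available. The supportable statement is that the variable is not named.
- **A reader might infer that group differences in endpoint 2 cannot be corrected.** That does not follow. In a chart review the variable can be added to the abstraction, and partial adjustment is possible with what is listed.
- **The numbers are assumptions.** Nothing in the documents indicates that use differed between groups or which envelope would be affected. The RR is applied to the whole composite, although endpoint 2 also covers pain, redness and migration. If only hematoma responds, the composite RR lies nearer 1.
- **The study is framed as descriptive.** Its objective is to gather information, and section 5 begins with tabulation. Section 5 also promises further comparisons between groups, which could include adjusted ones.

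The last point does not dispose of the matter. Section 5 commits to between-group tests, and its further comparisons name no method and no covariate. A row heading that could include a variable does not ensure uniform recording for every subject.

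**Conclusion.** The point holds in limited form. The plan names no determinant of endpoint 2 such as anticoagulant or antiplatelet use, and it compares non-randomized groups on pocket issues with unadjusted tests only. Followed as written, it leaves the endpoint 2 and hematoma comparisons open to confounding by bleeding risk.

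The size cannot be fixed from the documents. The illustrative ratios of about 1.1 to 1.7 require that antithrombotic use raises the risk of the composite by a factor of 1.5 to 3 and that its prevalence differs between groups by 20 to 50 percentage points. With no imbalance there is no bias from this source. The effect may therefore be minor or material, and unless use is recorded the results will not show which. This is a worthwhile, inexpensive improvement. It is not evidence that any envelope comparison is in fact wrong.

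**What to change.** - **Sections 2 and 2.1 (and the Synopsis list):** name anticoagulant use and antiplatelet use at implant (yes/no, class) as required baseline fields for every subject. If the case report form already holds them, say so in the protocol.
- **Section 5:** for endpoint 2, and separately for hematoma, add a group comparison stratified by or adjusted for antithrombotic use. Mantel-Haenszel would serve, or Firth (penalized) logistic regression if events are few. Limit the number of covariates by the event count, and state the rule in advance.
- **Reporting:** show this comparison beside the Fisher or Chi-square result, label that result unadjusted, and tabulate antithrombotic use by envelope group so that any imbalance is visible.

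Both parts are needed: recording the fields without an analysis that uses them would change no planned result. The cost is two or three fields read from charts already open, slightly longer abstraction for up to 700 subjects, and one added analysis. Patient management is unaffected.

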2.1 Schedule of Assessments

	Pre-Procedure Screening Visit	Procedure Visit	Follow-up Visits (up to 12 mo.)	Unscheduled Visit
Inclusion Determination	X			
Baseline Demographics	X			
Medical History/Risk Factors	X			
Type of Device Implanted		X		
Envelope Soak Solution Used		X		
Procedure Details		X		
Documentation of Complications		X		
Post-Operative Events			X	X
Infection Information/Culture Results			X	X
Pocket Related Issues			X	X

	TYPE: Protocol	Document	CPR-2212
	TITLE: RETROSPECTIVE EXPERIENCE OF CIED IMPLANTATION WITH PIEDMONT ATHENS REGIONAL ELECTROPHYSIOLOGY	Revision	C
		Page 7 of 9	

3. Study Objectives

The objective of the study is to:

1. The objective of this study is to retrospectively gather information on patients who underwent a CIED procedure with either a CanGaroo, Tyrx envelope, or no envelope.

Endpoints

The endpoints are defined as:

1. The incidence of major post procedure infection (as defined above)
2. Any pocket related issues that prompted an office visit which include but are not limited to pain, swelling, redness, migration and/or hematoma

4. Risks and Benefits

4.1.Risks

As this is a retrospective study, there are no physical potential risks to research subjects. There may be risks associated with loss of privacy.

